4.5 Toxicity Management

In response to AEs reported by study participants and/or observed upon exam by study staff, the investigator or designee will recommend either continuation or discontinuation of product use consistent with the criteria in Appendix II. Product use also will be discontinued in the event of pregnancy.

Participants who discontinue product use will not routinely be withdrawn from the study. Rather, every effort will be made to complete the safety evaluations scheduled to take place on study Days 7 and 14, and/or as specified in Appendix II.

4.6 Concomitant Medications

Enrolled study participants may continue use of all concomitant medications — except exclusionary antibiotics and preparations applied to the external genitalia or inserted into the vagina — during this study. All concomitant medications taken by participants throughout the course of the study — beginning with the Screening Visit — will be reported on applicable study case report forms. Medications used for the treatment of AEs that occur during study participation also will be recorded on applicable study case report forms.

4.7 **Procedures to be Followed in the Event of Pregnancy**

All participants will be instructed to report pregnancies to site investigator or to the study staff who will in turn report to the site investigator; the site investigator will inform the Protocol Team. The site investigator will counsel the participant and discuss possible risks if the pregnancy is continued. According to procedure included in the SSP Manual, the participant will be followed through the conclusion of her pregnancy, and live births will be followed for one year.

5.0 STUDY PROCEDURES

The study visit and procedures schedule is presented in Appendix I and described below. Detailed procedural instructions will be included in the Study-Specific Procedures Manual.

5.1 Screening Visit for Female Participants

(up to Day -42)

- Obtain written informed consent.
- Collect locator information, demographics, and medical history.
- Provide STD pre-test and HIV/STD risk reduction counseling; provide HIV pre-test counseling if medical records are not available to document HIV status.
- Collect urine and conduct pregnancy and leukocyte esterase (LE) test; if LE test is positive (greater than trace), perform culture and microscopy at the local laboratory (LL). Ship urine for chlamydia and gonorrhea nucleic acid amplification testing (NAT) at the HPTN Central Laboratory (CL).

- Perform symptom-directed physical exam.
- Perform pelvic exam, as follows:
 - naked eye exam of external genitalia,
 - speculum exam of vagina and cervix,
 - vaginal pH,
 - dried smear for Gram stain,
 - wet mount for trichomonas, candida, and BV,
 - sno-strip and cervicovaginal lavage (CVL) for HIV viral load at the HPTN CL,
 - Pap smear (unless medical records document a normal result in the past three months),
 - bimanual exam for adnexal or fundal masses or tenderness.

Note: Participants with abnormal Pap smear results will be referred for treatment

- Collect blood and perform the following at the LL:
 - complete blood count (CBC),
 - CD4+ cell count,
 - liver function testing (ALP, ALT, AST, GGT, total bilirubin),
 - renal function testing (BUN, creatinine),
 - coagulation testing (PT, APTT),
 - syphilis serology (RPR, with confirmation by FTA-ABS or MHA-TP),
 - HIV serology (EIA/WB), if HIV status is not adequately documented in available medical records,
 - process and ship plasma for HIV RNA polymerase chain reaction (PCR) at the CL.
- Provide the participant with:
 - instructions regarding the study behavioral requirements,
 - instructions to contact study staff to ask questions and report onset of menses,
 - instructions to inform her male sexual partner regarding her potential participation in the study and it's behavioral requirements (cohorts 3 and 4 only),
 - practice Daily Study Records and instructions for use, and
 - male condoms.
- Schedule next visit.
- Complete and submit required data collection forms.

5.2 Enrollment Visit for Female Participants

(**Day 0**)

- Update locator information.
- Verify that male sexual partner is eligible for the study and has provided written informed consent for study participation (cohorts 3 and 4 only).
- Provide results of all screening tests and post-test counseling.
- Administer baseline behavioral assessment .
- Review practice Daily Study Records.
- Collect urine and conduct pregnancy and LE test; if LE test is positive (greater than trace), perform culture and microscopy at the LL.
- Perform pelvic exam with colposcopy, as follows:
 - naked eye exam of external genitalia,
 - speculum exam of vagina and cervix,
 - colposcopic exam and imaging of vulva, vagina, and cervix,
 - vaginal pH,
 - dried smear for Gram stain,
 - wet mount for trichomonas, candida, and BV,
 - sno-strip and CVL for HIV viral load at the HPTN CL, and
 - bimanual exam for adnexal or fundal masses or tenderness.
- Collect blood and perform CBC, liver and renal function testing, coagulation testing, and plasma and serum archive at the LL; process plasma for HIV RNA PCR at the HPTN CL.
- Obtain and document random assignment.
- Provide the participant with:
 - supplies of the assigned study product,
 - instructions regarding the study behavioral requirements,
 - instructions to contact study staff to ask questions and/or report AEs,
 - Daily Study Records and instructions for use,
 - panty liners, and
 - male condoms.
- Schedule next visit.
- Complete and submit required data collection forms.

5.3 Enrollment Visit for Male Partners

(Day -42 to Day 0)

- Obtain written informed consent.
- Collect demographic and locator information.
- Collect information on STD history during the past six months and STD symptoms within the prior two weeks; perform genital exam if participant reports STD symptoms within the prior two weeks or if the participant requests an exam.
- If medical records are not available to document HIV status:
 - provide HIV pre-test counseling,
 - collect blood for HIV serology, and
 - deliver test results and post-test counseling when results are available.

Note: If HIV testing is required, enrollment of both the female participant and the male partner must be deferred until the HIV status of both partners is confirmed.

- Provide the participant with:
 - male condoms and HIV/STD risk reduction counseling,
 - instructions regarding the study behavioral requirements, and
 - instructions to contact study staff to ask questions and/or report AEs.
- Schedule acceptability interview
- Complete and submit required data collection forms.

5.4 Day 7 Follow-up Visit for Female Participants

(target Day 7, allowable Day 5-9)

- Update locator information.
- Collect used and unused product applicators, review the participant's Daily Study Records, and obtain interval medical history to assess adherence with protocol requirements and determine whether any AEs occurred since the last visit.
- Collect urine and conduct pregnancy and LE test; if LE test is positive (greater than trace), perform culture and microscopy at the LL.

- Perform pelvic exam with colposcopy, as follows:
 - naked eye exam of external genitalia,
 - speculum exam of vagina and cervix,
 - colposcopic exam and imaging of vulva, vagina, and cervix,
 - vaginal pH,
 - dried smear for Gram stain,
 - wet mount for trichomonas, candida, and BV,
 - sno-strip and CVL for HIV viral load at the HPTN CL, and
 - bimanual exam for adnexal or fundal masses or tenderness.
- Follow up on any abnormalities observed according to Appendix II.
- Collect blood and perform CBC, liver and renal function testing, and coagulation testing at the LL; process plasma for HIV RNA PCR at the HPTN CL.
- Provide the participant with:
 - supplies of the assigned study product,
 - instructions regarding the study behavioral requirements,
 - instructions to contact study staff to ask questions and/or report AEs,
 - Daily Study Records and instructions for use,
 - panty liners, and
 - male condoms.
- Schedule next visit.
- Complete and submit required data collection forms.

5.5 Day 14 Follow-up Visit for Female Participants

(target Day 14, allowable Day 12-16)

- Update locator information.
- Administer follow-up acceptability assessment and study burden assessment.
- Collect used and unused product applicators, review the participant's Daily Study Records, and obtain interval medical history to assess adherence with protocol requirements and determine whether any AEs occurred since the last visit.
- Collect urine and conduct pregnancy and LE test; if LE test is positive (greater than trace), perform culture and microscopy at the LL.

- Perform pelvic exam with colposcopy, as follows:
 - naked eye exam of external genitalia,
 - speculum exam of vagina and cervix,
 - colposcopic exam and imaging of vulva, vagina, and cervix,
 - vaginal pH,
 - dried smear for Gram stain,
 - wet mount for trichomonas, candida, and BV,
 - sno-strip and CVL for HIV viral load at the HPTN CL, and
 - bimanual exam for adnexal or fundal masses or tenderness.
- Follow up on any abnormalities observed according to Appendix II.
- Collect blood and perform CBC, liver and renal function testing, and coagulation testing at the LL; process plasma for HIV RNA PCR at the HPTN CL.
- Complete and submit required data collection forms.

5.6 Acceptability Interview for Male Partners

After female participants have completed product use, their male partners will complete a structured interviewer-administered acceptability assessment regarding their perceptions of the gel and of taking part in the study. Individual interviews will be conducted either in a face-to-face setting or by phone and will be carried out within four weeks following completion of product use.

5.7 Interim Contacts and Visits

Interim contacts and visits may be performed at participant request or as deemed necessary by the Investigator at any time during the study. All interim contacts and visits will be documented in participants' study records and on applicable case report forms.

Some interim visits may occur for administrative reasons. For example, the participant may have questions for study staff or require additional study supplies. Other interim contacts and visits may occur in response to AEs experienced by study participants. When interim contacts or visits are completed in response to participant reports of AEs, study staff will assess the reported event clinically and provide or refer the participant to appropriate medical care; all AEs associated with genital symptoms will be evaluated according to the pelvic exam procedures described for the Day 7 and Day 14 Follow-up Visits, and diagnosis and follow-up of any observed abnormalities will proceed according to Appendix II.

5.8 Unblinding Contact

After all participants have completed the study, and analyses of study data have been completed, the SDMC will provide the Investigator with information on each participant's product assignment. If desired by individual participants, site staff may then contact participants (e.g., by phone, fax, e-mail, in-person visit) to inform them of the product to which they were assigned.

6.0 SAFETY MONITORING AND ADVERSE EXPERIENCE REPORTING

6.1 Safety Monitoring

Close cooperation between the study team members will be necessary in order to monitor participant safety and respond to occurrences of toxicity in a timely manner. The team will meet via conference call every two weeks during the period of study implementation, and additional ad hoc calls will be convened if required.

The study site Investigators are responsible for continuous close monitoring of all AEs that occur among study participants, and for alerting the rest of the protocol team if unexpected concerns arise. In particular, Investigators will immediately report to the protocol team the occurrence of any grade 3 or higher AE (as defined by the DAIDS Toxicity Tables) judged possibly, probably, or definitely related to product use.

Accrual will be suspended if two or more participants in any cohort experience a grade 3 or higher AE judged possibly, probably, or definitely related to product use. An independent statistician then will review all data pertinent to these AEs – including the participants' random assignments. If the participants who experienced the AEs were assigned to different study products, the statistician will recommend to the study team that the study continue (without providing any further information that would unblind the team). If the participants who experienced the AEs were assigned to the same study product, the study team will be unblinded and the following actions will be undertaken:

- If the participants who experienced the AEs were assigned to the control gel, the protocol will be amended to eliminate application of the control gel.
- If the participants who experienced the AEs were assigned to CS gel, the study team will review all available safety data and determine whether to allow the study to proceed. A decision to stop the study may be made at this time or at any such time that the team agrees that an un acceptable type and/or frequency of AEs has been observed.

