- At enrollment is being treated for any STD.

DATE: 01 August 2003

RE: LETTER OF AMENDMENT FOR: HPTN 049, Version 2.0, dated 11 January 2003.

Phase I Safety and Acceptability Study of the Vaginal Microbicide 6% Cellulose Sulfate Gel Among HIV-Infected Women

- TO: ______, Principal Investigator, HPTU PTN XX-XXX
- FROM: [name], CORE Protocol Specialist

THE FOLLOWING INFORMATION IMPACTS THE HPTN 049 STUDY AND MUST BE FORWARDED TO YOUR INSTITUTIONAL REVIEW BOARD (IRB)/ETHICS COMMITTEE (EC) AS SOON AS POSSIBLE FOR THEIR INFORMATION AND REVIEW. THIS MUST BE APPROVED BY YOUR IRB/EC BEFORE IMPLEMENTATION.

THE FOLLOWING INFORMATION MAY ALSO IMPACT THE SAMPLE INFORMED CONSENT. YOUR IRB/EC WILL BE RESPONSIBLE FOR DETERMINING THE PROCESS OF INFORMING SUBJECTS OF THE CONTENTS OF THIS LETTER OF AMENDMENT.

PLEASE FILE THIS LETTER AND ANY IRB/EC CORRESPONDENCE IN YOUR REGULATORY FILE AND OTHER PERTINENT FILES. YOU ARE NOT REQUIRED TO SUBMIT THESE DOCUMENTS TO THE PROTOCOL REGISTRATION OFFICE UNLESS THE CHANGES RESULT IN A CHANGE TO THE INFORMED CONSENT FOR YOUR SITE.

Summary of Revisions

- The number of participants in Cohort 3 has been reduced from 24 to 12, and the number of participants in Cohort 4 has been reduced from 24 to 20 due to the low number of HIV infected sero-concordant couples that meet entry criteria and are interested in participating in the study.
- The study duration has been extended to 19 months.
- Other administrative clarifications have been incorporated in the protocol as needed.

Upon receipt of IRB approval, the following protocol modifications, indicated by strikethrough and **bold** text, will be implemented:

1. In the protocol Schema:

Treatment Regimen: Female participants will apply 3.5 mL of either 6% cellulose sulfate gel or a control gel intravaginally once or twice daily for 14 intramenstrual days, as follows:

Study Cohort	n CS gel	n Control gel	Frequency of Use
1: Sexually Abstinent	12	12	Once Daily
2: Sexually Abstinent	12	12	Twice Daily
3: Sexually Active and their male sexual partners	12 6	12 6	Once Daily
4: Sexually Active and their male sexual partners	12 10	12 10	Twice Daily

Study Duration: Accrual will require up to ++ 18 months. Each female participant will be followed for 14 days of product use and the entire study should be completed within ++3 19 months.

2. In the protocol Section 2.4.1:

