 - Within each cohort of 24 participants accrued across sites (24 each in Cohorts 1 and 2, 12 in Cohort 3 and 20 in Cohort 4), if two women experience a grade 3 AE judged possibly, probably, or definitely related to product use, accrual will be suspended at all sites and a safety data review will be undertaken to determine whether to continue the study, as described in Section 6.1. AEs will be defined as in Section 6 and graded according to the DAIDS Serious Adverse Experience (SAE) Reporting Manual for the HPTN and the DAIDS Toxicity Table.
- 4. In the protocol Section 3.0:

Up to 96 80 HIV-infected women will be included in this study, as will up to 48 32 HIV-infected male partners of sexually active female participants. Participants will be selected for the study according to the criteria in Section 3.1 and 3.2. They will be recruited as described in Sections 3.3 and 3.4 and assigned to a study product group as described in Section 7.4. Participant retention procedures are described in Section 3.6 and conditions for withdrawal from the study are described in Section 3.7.

5. In the protocol Section 3.4, third paragraph:

Women found to be presumptively eligible at the Screening Visit will be scheduled for an Enrollment Visit to take place 3-5 **2-6** days following **the end of** their next menstrual period, but within 42 days of the Screening Visit. (Women who are not enrolled within 42 days of screening must repeat all screening evaluations.) At this visit, female participants' eligibility will be confirmed according to the procedures described in Section 5.2; confirmed eligible participants will be randomized (see Section 7.4) and enrolled in the study.

6. In the protocol Section 7.3:

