As noted in Section 2.4 up to 96 **80** female participants and up to 48 **32** male partners will be included in this study. Female participants will be enrolled into four cohorts, of 24 women each, Cohorts 1 and 2 consisting of 24 women each, Cohort 3 consisting of 12 women, and Cohort 4 consisting of 20 women. Within each cohort Cohorts 1 and 2, accrual of six participants at each of the four study sites is targeted, within Cohort 3, accrual of three participants at each of the four sites is targeted, and with Cohort 4, accrual of 5 participants at each of the four study sites is targeted. If for some reason a site experiences difficulty reaching its accrual targets, consideration will be given to shifting enrollment "slots" to the other sites, with prior approval of the Protocol Chair.

Ideally, at At each site, three of the six participants enrolled in each cohort, Cohorts 1 and 2, at most two of the three participants enrolled in Cohort 3, and at most three of the five participants enrolled in Cohort 4 will be assigned at random to apply CS gel at the assigned frequency (once or twice daily). The other three women in each cohort will be assigned to apply the control gel. Also at each site, accrual of each cohort will proceed sequentially, after the completion of follow-up of all participants in the prior cohorts, provided accrual is not suspended per the provisions of Section 2.4.3.

As a means to characterize the statistical properties of this study Cohorts 1 and 2, the following table presents the probability of observing zero, at least one, and two or more safety endpoints among groups of 12 women for various "true" event rates:

Event Rate	P (0 events n=12)	P (≥1 event n=12)	P (> 2 events n=12)
1%	0.89	0.11	0.01
5%	0.54	0.46	0.12
10%	0.28	0.72	0.34
15%	0.14	0.86	0.56
25%	0.03	0.97	0.84
35%	0.01	0.99	0.96
45%	< 0.01	>0.99	0.99

For example, if the true rate of a given endpoint in **Cohorts 1 or 2** is five percent, the probability that the endpoint will be observed in at least one of 12 women is 0.46. In addition, with a true rate of five percent, 12 women provide 88 percent power to exclude endpoint rates greater than 35 percent (i.e., the probability of observing 0 or 1 endpoint is less than 0.05 when the true rate is 35 percent, while this probability is 0.88 when the true rate is five percent).

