2.4.3 Cohort Progression

The study will begin with accrual of sexually abstinent participants into Cohort 1. Thereafter, accrual and follow-up will proceed according to the following guidelines:

• Sequential accrual into Cohorts 2, 3, and 4 may begin upon completion of follow-up of all participants in the prior cohorts.

• Within each cohort of 24 participants accrued across sites, if two women experience a grade 3 AE judged possibly, probably, or definitely related to product use, accrual will be suspended at all sites and a safety data review will be undertaken to determine whether to continue the study, as described in Section 6.1. AEs will be defined as in Section 6 and graded according to the DAIDS Serious Adverse Experience (SAE) Reporting Manual for the HPTN and the DAIDS Toxicity Table.

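### The only mandatory safety review by gel needs two related grade 3+ AEs in one cohort; the count restarts in each cohort, stayed at two when the arms shrank, and no by-gel look precedes escalation

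*Protocol*

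**What the plan says.** Protocol 6.1 (Safety Monitoring) sets the trigger: "Accrual will be suspended if two or more participants in any cohort experience a grade 3 or higher AE" that is judged at least possibly related. The independent statistician then reviews the data on those events with the assignments. If the events are on different gels, the statistician recommends continuing. If they are on the same gel, the team is unblinded. Two control-gel events then lead to an amendment dropping the control gel; two CS events lead to a full safety review by the team.

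Section 2.4.3, as rewritten by item 3 of the Letter of Amendment of 01 August 2003, lists the new cohort sizes ("24 each in Cohorts 1 and 2, 12 in Cohort 3 and 20 in Cohort 4") and keeps the threshold: "if two women experience a grade 3 AE judged possibly, probably, or definitely related to product use, accrual will be suspended at all sites". The same letter records that "The number of participants in Cohort 3 has been reduced from 24 to 12"; Cohort 4 went from 24 to 20. The CS arms are now 12, 12, 6 and 10.

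On escalation, 2.4.3 says: "Sequential accrual into Cohorts 2, 3, and 4 may begin upon completion of follow-up of all participants in the prior cohorts". Section 7.3 adds a second condition, "provided accrual is not suspended per the provisions of Section 2.4.3", and introduces the sequence with the words "Also at each site, accrual of each cohort will proceed sequentially".

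Section 6.1 also requires investigators to report every related grade 3+ AE to the protocol team at once, schedules team calls every two weeks, and lets the team stop the study whenever it finds the type or frequency of AEs unacceptable. Section 10.2 has the team, and CORE and SDMC representatives, watch AE incidence. Section 7.5 keeps study staff blinded until visits and analyses are complete, apart from 6.1 and individual safety exceptions.

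**The concern.** This is a frequency-escalation study with toxicity as its primary aim, so the moments that matter are the openings of Cohorts 2, 3 and 4. At none of them does the protocol require anyone to compare the gels. The only required comparison depends on two events falling within the same cohort.

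One related grade 3+ AE on CS gel in Cohort 1, another in Cohort 2 and a third in Cohort 4, with none on control, would leave the count at one each time. The blinded team would know of three events but not that all three were on CS gel.

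The smaller cohorts add to this. Two events are 2/12 = 17% of the CS arm in Cohorts 1 and 2, but 2/6 = 33% in Cohort 3 and 2/10 = 20% in Cohort 4. The amendment rewrote the relevant bullet without revisiting the threshold.

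**Working it through.** **Inputs.** CS arm sizes 12, 12, 6, 10 (amended Schema and 2.4.1); threshold two women per cohort (2.4.3, 6.1). The protocol gives no expected rate of related grade 3+ AEs. True rates of 5%, 10% and 25% are therefore assumptions, taken from the range of its own tables and held constant over cohorts, with women independent.

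**Reproducing the protocol.** P(≥2) = 1 − (1−p)^n − n·p·(1−p)^(n−1). At p = 25%: n = 12 gives 0.842 (stated 0.84), n = 6 gives 0.466 (stated 0.47), n = 10 gives 0.756 (stated 0.76). All cells of the three amended 7.3 probability tables reproduce. Going from 12 to 6 women lowers P(≥2) from 0.12 to 0.03 at 5%, from 0.34 to 0.11 at 10% and from 0.84 to 0.47 at 25%.

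**Chance that CS events alone trip the rule in some cohort.** 1 − product of P(≤1) over the four CS arms.
- 5%: 1 − 0.8816² × 0.9672 × 0.9139 = 0.313. With four arms of 12: 1 − 0.8816⁴ = 0.396.
- 10%: 1 − 0.6590² × 0.8857 × 0.7361 = 0.717. With four arms of 12: 0.811.
- 25%: 0.997. With four arms of 12: 0.999.

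**The gap: two or more CS events in total, never two in one cohort.** A CS-driven trigger implies at least two CS events overall, so the gap is P(≥2 of 40) minus the trigger probability.

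| True CS rate (assumed) | P(≥2 of 40) | CS-driven trigger | Gap |
|---|---|---|---|
| 5% | 0.601 | 0.313 | 0.29 |
| 10% | 0.920 | 0.717 | 0.20 |
| 25% | >0.99 | 0.997 | 0.003 |

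Exactly one CS event in all four cohorts is rare: 0.9%, 1.9% and 0.1% at these rates. The gap is mostly two or three scattered events.

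**Allowing for control events.** Women on both gels count toward the trigger. Per cohort with n women per gel, the no-trigger outcomes are no CS event with at most one control event, or one CS event with no control event. Multiplying these over the four cohorts and keeping outcomes with two or more CS events gives, at an assumed 1% control rate, a gap of 0.23 (5% CS) and 0.15 (10% CS). Overall suspension probabilities are then 0.41 and 0.77. At an assumed 5% control rate the gap is 0.08 and 0.05.

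A mixed-gel trigger does not fully close the gap. Suppose Cohorts 1 and 2 each had one CS event, and Cohort 3 had one CS and one control event. The Cohort 3 pair is on different gels, so 6.1 has the statistician recommend continuing. No stated duty brings the two earlier CS events into that comparison.

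**The case against.** The strongest case against is that review does not depend on the trigger. Every related grade 3+ AE reaches the team at once, the team confers every two weeks and may stop at any time, AE incidence is monitored under 10.2, and 7.5 allows individual unblinding for safety. All this stands. A reader might infer that CS events spread over four cohorts would never prompt any review; the documents do not support that. They would prompt blinded review. Two in any single cohort would suspend accrual, and escalation also requires that accrual is not suspended. What these provisions lack is a view by gel: the team is blinded, the 7.5 exception concerns individual cases, and 10.2 does not say that AE rates are examined by gel.

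Second, the cohorts differ in frequency of use and sexual activity, so counting within a cohort is a coherent choice. That defends the per-cohort trigger, but does not explain why nobody is asked to look across cohorts.

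Third, the 7.3 tables concern safety endpoints in general, which 7.2.1 defines far more broadly than related grade 3+ AEs; the higher rates in them may be unrealistic for this trigger. That is fair, and the gap nearly vanishes at 25% in any case. It is material at 5% to 10%.

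A reader might also take 7.3 to permit escalation site by site. Section 2.4.3 refers to all participants in the prior cohorts without any site limit, and 7.3 repeats that phrase, so this is an ambiguity to clear up and no more.

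**Conclusion.** The point holds in this form: no mandatory review by gel accumulates related grade 3+ AEs across cohorts, none is required before a new cohort opens, and the threshold of two was not revisited when the CS arm fell to 6 in Cohort 3 and 10 in Cohort 4. Counting CS events only, the chance of two or more with no trigger is 0.29, 0.20 and 0.003 at assumed true rates of 5%, 10% and 25%; counting control events makes it smaller. These figures rest on assumed rates, constant over cohorts. The loss of sensitivity in Cohort 3 (0.84 to 0.47 at 25%) comes from the protocol's own tables. This is a weakness in a design choice that can be repaired cheaply. It is not an absence of safety monitoring.

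**What to change.** In 2.4.3 and 6.1, require that before each new cohort opens the independent statistician, kept separate from the blinded team, reviews a closed tabulation by gel of related grade 3+ AEs and primary endpoints accumulated over all completed cohorts, and advises the team whether a full safety review is needed. State that this review does not by itself invoke the unblinding or control-gel removal steps of 6.1.

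Reconcile 7.3 with 2.4.3, so that it is clear whether follow-up must be complete across all sites. Reconcile also the grade wording: 2.4.3 refers to grade 3, while 6.1 refers to grade 3 or higher.

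The cost is a short pause and one extra closed tabulation before each of Cohorts 2, 3 and 4, using data already collected and a role already named.

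Simply applying the count of two cumulatively per gel is not advised. Under 6.1 two control events force removal of the control gel. The chance of reaching that count rises from 1.8% (per cohort) to 6.1% (cumulative over 40 women) at a true 1% control rate, and from 31% to 60% at 5%. With 1% on both gels, the chance of same-gel unblinding rises from 1 − (1 − 0.018)² = 3.6% to 1 − (1 − 0.061)² = 11.8%.
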